**LIST OF ABBREVIATIONS**

[figure not shown]
Examples Include:

AE	Adverse Event
ALT	Alanine Aminotransferase
ALC	Absolute Lymphocyte Count
ALL	Acute Lymphocytic Leukemia
AST	Aspartate Aminotransferase
BUN	Blood Urea Nitrogen
CBC	Complete Blood Count
CMP	Comprehensive Metabolic Panel
CLL	Chronic Lymphocytic Leukemia
CR	Complete Response
CT	Computed Tomography
CTCAE	Common Terminology Criteria for Adverse Events
CTU	Clinical Trials Unit
DLT	Dose Limiting Toxicity
DSMB	Data and Safety Monitoring Board
ECOG	Eastern Cooperative Oncology Group
H&P	History & Physical Exam
HRPP	Human Research Protections Program
IV (or iv)	Intravenously
MCL	Mantle Cell Lymphoma
MTD	Maximum Tolerated Dose
NCI	National Cancer Institute
ORR	Overall Response Rate
OS	Overall Survival
PBMCs	Peripheral Blood Mononuclear Cells
PCF	Pathcore Facility
PD	Progressive Disease
PFS	Progression Free Survival
p.o.	per os/by mouth/orally
PR	Partial Response
SAE	Serious Adverse Event
SD	Stable Disease
SGOT	Serum Glutamic Oxaloacetic Transaminase
SPGT	Serum Glutamic Pyruvic Transaminase
WBC	White Blood Cells

Study Numbers: NU 14H06  
PCI-32765MCL2003

Initial version: September 24, 2014  
AMD 11: ver. date 08.06.2022

## STUDY SCHEMA

Patients must receive at least 4 cycles of induction chemotherapy with or without auto-SCT, including R-CHOP (with or without alternating R-DHAP), R-Hyper-CVAD, or R-bendamustine.

Per Cheson 2007 criteria.

During treatment, 1 cycle = 28 days. Patients will be evaluated (and drug will be dispensed) prior to each cycle for the first 6 months, then every 3 cycles thereafter for the remainder of treatment. See section 4.2 for the provision of 6-month visits after 2 years.

Follow-up schedule for patients off-treatment will be every 3 months up to 2 years post-first dose, then every 6 months up to 4 years post-first dose. Date of progression will be documented as well.

Study Numbers: NU 14H06  
PCI-32765MCL2003Initial version: September 24, 2014  
AMD 11: ver. date 08.06.2022**STUDY SUMMARY**

Title	A Phase II Clinical Trial Evaluating Ibrutinib Maintenance Following Intensive Induction for Patients with Previously Untreated Mantle Cell Lymphoma (MCL)
Version Date	August 8, 2022 (Amendment 11)
Phase/Design	Phase II, single-arm, multicenter, open-label study
Study Center(s)	Lead site: Northwestern University Participating sites: University of Michigan, University of Utah, and Dana Farber d/b/a Massachusetts General Hospital
Objectives	
Primary objective: Determine the 3-year PFS in patients with previously-untreated MCL who achieve response to intensive induction therapy and then receive maintenance Ibrutinib.
 
Secondary objectives:
 
 
• Toxicity
 
• Rates of conversion from PR to CR
 
• Median overall survival at 4 years
 
 
Exploratory objectives: Monitor MRD results by PCR and correlate with PFS and OS.

Sample Size	36 evaluable patients (patients who receive < 1 complete cycle of therapy will not be considered evaluable for efficacy endpoints and will be replaced; we estimate this to represent 3 or fewer subjects)
Diagnosis and Main Inclusion Criteria	
 
1. Histologically confirmed MCL.
 
2. Disease response (either CR or PR), without known progression, to one (1) prior systemic chemotherapy regimen, with or without consolidative auto SCT. The options are:           
 
a. R-CHOP (with or without cytarabine-containing cycles, including "Nordic" [1] and MCL-NET protocols [2]) with or without auto SCT
 
b. R-Hyper-CVAD with or without auto SCT
 
c. R-Bendamustine with or without auto SCT
 
 
 
3. Prior radiotherapy is permissible.
 
4. Age <math>\geq</math> 18 years.
 
5. ECOG performance status <math>\leq</math> 2.
 

Treatment Plan	Ibrutinib will be given at a fixed dose of 560 mg PO daily throughout the study, to patients who have completed at least 4 cycles of intensive induction chemotherapy (with or without ASCT). The dose is based upon safety and efficacy data. For the purposes of this study, one cycle will be defined as 28 days. This will be continued up to 4 years in the absence of progression of disease, intolerable toxicity, or patient preference (including withdrawal of consent).

Study Numbers: NU 14H06  
PCI-32765MCL2003Initial version: September 24, 2014  
AMD 11: ver. date 08.06.2022

Statistical Methodology	
The primary endpoint is three-year PFS. Our null hypothesis is that ibrutinib maintenance will yield no improvement upon the 60% three-year PFS observed in studies described above. We consider an observed three-year PFS of 80% both feasible and of significant clinical improvement. The study will have 10% Type I error and 90% power to detect an effective treatment using a one-stage design based on the true proportion of patients achieving 3-year PFS is at least 80% versus the null hypothesis that the true complete response rate is at most 60%. Based upon these parameters, our sample size will be 36 evaluable patients. For the final analysis, if 25 or fewer patients are alive and without progression from among all 36 evaluable patients accrued, we will consider this regimen ineffective for this patient population. If, on the other hand, 26 or more patients are alive and without progression, this will be considered sufficient evidence that this treatment may be recommended for further testing in subsequent studies, particularly in a randomized setting.

--------------------------------	--

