## 4.0 TREATMENT PLAN

### 4.1 Overview

Induction therapy will not be part of the protocol-specified treatment. Patients must have received four (4) or more cycles of R-CHOP (with or without alternating R-DHAP), R-Hyper-CVAD, or bendamustine + rituximab (all with or without auto SCT), with documented PR or CR by Cheson 2007 criteria. Within 14 days of study registration, patients will begin treatment with ibrutinib at a fixed dose of 560 mg PO daily. One cycle will be defined as 28 days. Patients may continue to receive cycles of ibrutinib therapy up to 4 years in the absence of progression of disease or intolerable toxicity, or patient preference (including withdrawal of consent).

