#### **4.7 Duration of Follow Up**

Patients who complete 4 years of maintenance therapy with ibrutinib will have one final follow-up study visit approximately 30 days post-last dose. Patients who discontinue study therapy prior to this point will be followed up to a maximum of 4 years (post-first dose of treatment) for survival endpoints (including date of progression). Follow-up will occur every 3 months (up to 2 years after the first dose of treatment) and then every 6 months thereafter (up to 4 years post-first dose).

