#### 6.2.3 Median overall survival at 4 years

Overall survival (OS) will be defined as the duration of time from start of treatment up to 4 years from the start of study treatment.

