## **10.2 Sample Size and Power Calculations**

The primary endpoint is three-year PFS. Our null hypothesis is that ibrutinib maintenance will yield no improvement upon the 60% three-year PFS observed in

studies described above. We consider an observed three-year PFS of 80% both feasible and of significant clinical improvement. The study will have 10% Type I error and 90% power to detect an effective treatment using a one-stage design based on the true proportion of patients achieving 3-year PFS is at least 80% versus the null hypothesis that the true complete response rate is at most 60%.

Based upon these parameters, our sample size will be 36 evaluable patients. For the final analysis, if 25 or fewer patients are alive and without progression from among all 36 evaluable patients accrued, we will consider this regimen ineffective for this patient population. If, on the other hand, 26 or more patients are alive and without progression, this will be considered sufficient evidence that this treatment may be recommended for further testing in subsequent studies, particularly in a randomized setting.

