#### **10.3.2 Secondary Objectives**

To assess toxicity, all adverse events will be summarized as to type, severity, frequency, timing and attribution. Descriptive frequencies and proportions will be used for this analysis.

To determine rates of conversion from PR to CR, only patients who had a PR at the time of registration and who complete  $\geq 1$  complete cycle of ibrutinib maintenance therapy will be evaluable for this endpoint. These rates will be calculated as a proportion together with exact 90% confidence limits.

To determine median overall survival (OS) after 4 years, Kaplan-Meier curves will be determined for overall survival and the five-year point on this curve, along with 90% confidence limits, will be determined. Patients will be evaluated monthly for the first 6 months on treatment, then every 3 months thereafter. Patients who go off treatment will continue to be followed for survival up to a maximum of 4 years post-first dose. Follow-up will occur every 3 months (up to 2 years after the first dose of treatment) and then every 6 months thereafter (up to 4 years post-first dose).

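### The overall survival analysis set is not stated, and the only general evaluability rule, read literally, would leave first-cycle deaths out of a curve timed from first dose

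*Combined protocol and SAP*

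**What the plan says.** **The general rule.** In the Sample Size row of the Study Summary, patients with less than one complete cycle "will not be considered evaluable for efficacy endpoints and will be replaced". Their expected number is given as: "we estimate this to represent 3 or fewer subjects". Section 3.0 defines the 36 evaluable subjects by the same one-complete-cycle criterion, and Section 6.2.1 still mentions patients who are replaced for efficacy. Section 4.1 gives the cycle length: "One cycle will be defined as 28 days".

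**Endpoints with their own set.**
- PFS (6.1): any patient with at least one dose, in a sentence limited to that endpoint.
- Toxicity (6.2.1): at least one dose, replaced patients included.
- PR-to-CR conversion (6.2.2 and 10.3.2): PR at registration and at least one complete cycle.

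**Overall survival.** Section 6.2.3 defines OS as "the duration of time from start of treatment up to 4 years from the start of study treatment". Section 10.3.2 says "Kaplan-Meier curves will be determined for overall survival". On follow-up, Section 4.7 says "Patients who discontinue study therapy prior to this point will be followed up to a maximum of 4 years", counted from first dose, with no minimum exposure. None of 2.2.3, 6.2.3, 10.1.2 or 10.3.2 says which patients are analysed.

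**History.** In Appendix IV, the Amendment 4 entry for Section 6.1 explains the move to a one-dose rule by describing the design as intention to treat. That entry is logged against 6.1 only.

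**The concern.** OS is the only primary or secondary endpoint without a stated population, so a statistician looking for one falls back on the general rule. Under that rule, entry to the curve depends on something that happens after time zero, namely completing cycle 1. A patient who dies before day 28 cannot have completed a cycle, so that patient is removed and replaced by someone who did complete one. Survival through the first cycle is then 100% by construction, which is immortal time.

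Two consequences follow. A first-cycle death could be a PFS event under 6.1 and yet be absent from OS, so the two curves would describe different patients. And two analysts could draw different OS curves from the same protocol, with the choice possibly made after early deaths are known. The same undefined set feeds the regression of OS on minimal residual disease in 10.3.3.

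**Working it through.** **1. The plan's own design figure.** Section 10.2 states: "The study will have 10% Type I error and 90% power to detect an effective treatment using a one-stage design". It continues: "Based upon these parameters, our sample size will be 36 evaluable patients". Success is 26 or more alive and progression-free, with 60% against 80%. With X binomial(36, p):
- P(X ≥ 26 | p = 0.60) = 0.0904
- P(X ≥ 26 | p = 0.80) = 0.9111

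The stated 10% and 90% are reproduced. No OS quantity enters this calculation, and the plan gives no design figure for OS.

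**2. Inputs for OS.**
- Patients kept under the one-cycle rule: 36 (Section 10.2).
- Patients replaced: 0 to 3 (Study Summary), so at most 39 treated.
- 4-year OS among the 36 kept, S: not in the documents. Assumed range 60% to 90%.

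**3. Survival at day 28.** If k excluded patients died in cycle 1, survival at day 28 among all treated is 36/(36 + k): 97.3% for k = 1, 94.7% for k = 2 and 92.3% for k = 3. The literal rule reports 100% each time.

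**4. 4-year OS when the k excluded patients died.** All-treated OS = S × 36/(36 + k). The fall from S, in points, is in brackets.

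| S in the 36 kept | k = 1 | k = 2 | k = 3 |
|---|---|---|---|
| 60% | 58.4% (1.6) | 56.8% (3.2) | 55.4% (4.6) |
| 70% | 68.1% (1.9) | 66.3% (3.7) | 64.6% (5.4) |
| 80% | 77.8% (2.2) | 75.8% (4.2) | 73.8% (6.2) |
| 90% | 87.6% (2.4) | 85.3% (4.7) | 83.1% (6.9) |

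For deaths in the first 28 days this carries over to the Kaplan-Meier estimate, provided nobody is censored in that window. For excluded patients who die later, it assumes that they are followed to 4 years.

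**5. The other direction.** If three patients are replaced and all are alive at 4 years, all-treated OS = (36 × S + 3)/39:
- S = 60%: 24.6/39 = 63.1%, so the reported figure is 3.1 points too low.
- S = 85%: 33.6/39 = 86.2%, 1.2 points too low.
- S = 90%: 35.4/39 = 90.8%, 0.8 points too low.

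**6. No effect.** If nobody is replaced, or if replaced patients survive at the same rate, (36 × S + 3 × S)/39 = S and the 4-year figure does not move.

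**The case against.** The strongest reply is that the protocol already points to an all-treated OS analysis. Section 10.3.2 writes the one-cycle limit into the PR-to-CR paragraph and leaves it out of the OS paragraph that follows. That OS paragraph, like 2.2.3 and 4.7, follows patients who leave treatment for survival, whatever their exposure. The Amendment 4 rationale calls the design intention to treat. On this view the Summary wording is a leftover.

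This stands as evidence of intent. A reader might infer from the Summary that first-cycle deaths will certainly drop out of OS. The documents do not support that: exclusion is the literal reading of an unspecified set, not a settled result. But follow-up text says whose data are collected, not who enters the curve, and the amendment rationale is a log entry for PFS. The contrary wording is current in the Summary, Section 3.0 and 6.2.1.

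A reader might also infer that the rule can only hide deaths. It cannot be said so generally. Patients who stop within a cycle for toxicity or by choice and then survive would also be excluded, which lowers reported OS (step 5).

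The effect is also modest against sampling error. At 85% OS with 36 patients, an approximate 90% interval has half-width 1.645 × √(0.85 × 0.15/36), or about 10 points. The three-death case is an extreme, because the plan's estimate of three counts early stopping for any reason. First-cycle deaths would also remain visible as PFS events, in the toxicity summary and as serious adverse events.

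**Conclusion.** The point holds as a gap in specification with a possible bias. The OS set is undefined, and the only general rule that could fill the gap conditions on completing cycle 1 while the clock starts at first dose.

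Under an assumed 4-year OS of 60% to 90% in the kept patients, reported OS would be too high by 1.6 to 2.4 points for each excluded patient who died. It would be too high by at most 4.6 to 6.9 points if all three replaced patients died. It would be too low by 0.8 to 3.1 points if all three survived, and unchanged if nobody is replaced or if replaced patients fare like the rest.

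It would be wrong to extend this to the trial's conclusion. OS is secondary and has no hypothesis or decision rule, so the choice of OS set does not touch the 26-of-36 test. Nor does the general rule govern PFS in the endpoint section, since 6.1 sets its own one-dose rule.

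**What to change.** In 6.2.3 and 10.3.2, add: *Overall survival will be analysed in all patients who receive at least one dose of ibrutinib, including patients who are replaced, from the date of first dose.*

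In the Study Summary and Section 3.0, limit the one-complete-cycle criterion to PR-to-CR conversion and bring the wording into line with 6.1 and 6.2.1. Merely exempting OS in the Summary would not do. It would make OS the only exception and so imply that PFS is under the one-cycle rule, against 6.1. Whether early stoppers are still replaced to reach 36 is a separate matter for the primary analysis, and the OS sentence works either way.

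The cost is a few sentences, with no new procedures, because survival follow-up after early discontinuation is already required by 4.7. The reported OS figure may change slightly in either direction. The wording should be settled before OS is analysed.

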## 1.0 BACKGROUND AND RATIONALE

### 1.1 Disease Background & Current Therapies

Mantle cell lymphoma (MCL) is an uncommon B-cell non-Hodgkin lymphoma (NHL) that carries a poor overall prognosis in spite of high response rates to induction chemotherapy [3, 4]. It accounts for about 6% of all NHL cases in the Western world. At the molecular level, MCL is uniquely characterized by overexpression of the cell cycle regulator protein cyclin D1. This is due to the chromosomal translocation t(11;14)(q13;q32), which puts the cyclin D1 gene, B-cell leukemia/lymphoma 1 (bcl-1), under the control of the immunoglobulin heavy chain enhancer with subsequent overexpression of cyclin D1 [5-7].

Although there is no consensus as to the ideal frontline therapy for MCL, aggressive multi-agent chemoimmunotherapy combinations such as R-CHOP (rituximab with cyclophosphamide, doxorubicin, vincristine, and prednisone) have been advocated. More intensive regimens, such as Hyper-CVAD (hyperfractionated cyclophosphamide, vincristine, doxorubicin, and dexamethasone alternating with methotrexate and cytarabine) or other regimens that incorporate high-dose cytarabine [1, 2], may improve outcomes, though this has not been clearly shown and toxicity with such regimens is clearly increased[8]. Younger patients with good performance status are frequently considered for more intensive induction therapy followed by consolidation therapy with autologous stem cell transplant (ASCT); however, this degree of intensive therapy is not an option for most patients with MCL because of their age and comorbidities[9, 10].

Multiple prospective and retrospective trials have demonstrated patterns of continuous response over many months and years, suggesting that all patients are at risk for eventual relapse [3, 4, 11]. Once the disease has progressed after first-line therapy, the prognosis is dismal.

The best estimates of 3-year progression-free survival (PFS) in patients with MCL treated with R-Hyper-CVAD (Rituximab-Hyper-CVAD) in multicenter studies are 58-64% [11]. Likewise, consolidation with high-dose therapy (HDT) and ASCT after R-CHOP also seems to improve depth and duration of responses as compared to R-CHOP, but does not clearly improve overall survival. Interestingly, an retrospective analysis of patients treated at National Comprehensive Cancer Network (NCCN) Centers suggested that patients treated with Hyper-CVAD had similar outcomes to those treated with R-CHOP followed by HDT-ASCT, but that HDT-ASCT did not improve outcomes when used as consolidation after induction with R-Hyper-CVAD [11].

Maintenance strategies have previously been studied in patients with MCL. For example, a phase III European study randomized patients with previously untreated MCL, who achieved a response to R-CHOP, to maintenance treatment of either rituximab or interferon, and showed improved median PFS and OS among those on the rituximab arm [12].

Ibrutinib is a selective BTK inhibitor that has demonstrated profound activity in patients with relapsed/refractory MCL, with an overall response rate (ORR) of 68% and median PFS of 13.9 months [13]. Ibrutinib was approved by the Food

Study Numbers: NU 14H06  
PCI-32765MCL2003Initial version: September 24, 2014  
AMD 11: ver. date 08.06.2022

and Drug Administration (FDA) in November 2013 as single agent treatment for patients with MCL who have received at least one prior therapy. It has since been approved for CLL/SLL, CLL/SLL with 17p deletion, and Waldenström's macroglobulinemia. The drug is well tolerated, with neutropenia and gastrointestinal disturbances as its chief adverse effects. Ibrutinib is now the focus of multiple combination treatment trials. However, there is no reported data for the role of ibrutinib as maintenance therapy after response to other treatment.

## 1.2 Ibrutinib Background and Toxicities

Ibrutinib, an irreversible inhibitor of BTK, has been shown to have potent inhibitory and anti-proliferative activity, in cell line as well as in vivo mouse xenograft models of B-cell malignancies such as ALL and CLL. Inhibition of BTK activity interrupts cellular signaling processes that control cell division in B-cells. The pharmacology and toxicology of ibrutinib in animal models are detailed in the Investigator's Brochure.

In an open-label drug-drug interaction study of 18 men, ibrutinib was administered alone at a 120 mg dose or in combination with ketoconazole at a 40 mg dose. Preliminary results demonstrated a mean 25-fold increase in ibrutinib area under the plasma concentration-time curve (AUC) and a 29-fold increase in Cmax following co-administration with ketoconazole. Terminal half-life was not increased. Ibrutinib single-dose administration was well-tolerated. No drug-related adverse events were reported. No Grade 3 or 4 toxicities or serious adverse events were reported.

### 1.2.1 Preclinical & pharmacokinetic data

#### 1.2.1.1 Mechanism of Action

Ibrutinib is a small-molecule inhibitor of BTK. Ibrutinib forms a covalent bond with a cysteine residue in the BTK active site, leading to inhibition of BTK enzymatic activity. BTK is a signaling molecule of the B-cell antigen receptor (BCR) and cytokine receptor pathways. BTK's role in signaling through the B-cell surface receptors results in activation of pathways necessary for B-cell trafficking, chemotaxis, and adhesion. Nonclinical studies show that ibrutinib inhibits malignant B-cell proliferation and survival in vivo as well as cell migration and substrate adhesion in vitro.

#### 1.2.1.2 Pharmacodynamics

In patients with recurrent B-cell lymphoma > 90% occupancy of the BTK active site in peripheral blood mononuclear cells was observed up to 24 hours after ibrutinib doses of  $\geq 2.5$  mg/kg/day (175 mg/day for average weight of 70 kg).

#### 1.2.1.3 Pharmacokinetics

##### Absorption

Ibrutinib is absorbed after oral administration with a median Tmax of 1 to 2 hours. Ibrutinib exposure increases with doses up to 840 mg. The steady-state AUC observed in patients at 560 mg is

Study Numbers: NU 14H06  
PCI-32765MCL2003

Initial version: September 24, 2014  
AMD 11: ver. date 08.06.2022

(mean  $\pm$  standard deviation)  $953 \pm 705$  ng/mL. Administration with food increases ibrutinib exposure approximately 2-fold compared with administration after overnight fasting.

#### Distribution

Reversible binding of ibrutinib to human plasma protein in vitro was 97.3% with no concentration dependence in the range of 50 to 1000 ng/mL. The apparent volume of distribution at steady state ( $V_d,ss/F$ ) is approximately 10000 L.

#### Metabolism

Metabolism is the main route of elimination for ibrutinib. It is metabolized to several metabolites primarily by cytochrome P450, CYP3A, and to a minor extent by CYP2D6. The active metabolite, PCI-45227, is a dihydrodiol metabolite with inhibitory activity towards BTK approximately 15 times lower than that of ibrutinib. The range of the mean metabolite to parent ratio for PCI-45227 at steady-state is 1 to 2.8.

